### Abbreviations

AE	Adverse Event
AKI	acute kidney injury
AUC	area under the concentration curve
CHF	Congestive Heart Failure
CKD	chronic kidney disease
CPK	creatine phosphokinase
CRF	Case Report Form
DAC	data adjudication committee
eGFR	estimated Glomerular Filtration Rate
ePV	estimated plasma volume
eTBV	estimated total blood volume
EOS	end of study
GFR	Glomerular Filtration Rate
hcg	human chorionic gonadotropin
IB	Investigators Brochure
ICU	Intensiv Care Unit

IMP	investigational medicinal product
ITT	Intent to treat Population
mGFR	Measured Glomerular Filtration Rate
mPV	measured Plasma Volume
mTBV	measured total blood volume
NYHA	New York Heart Association
PPP	Per protocol population
PV	Plasma Volume
SAE	Serious Adverse Event
TBV	total blood volume
TEAE	treatment-emergent adverse event
VFI	Visible fluorescent injectate (FD004)
WOCBP	Women of child-bearing potential

Study Physician / member of the trial team
 
Trial Statistician
	

Hypotheses
	
It is hypothesized that utilizing the FAST PV and mGFR Technology™ is safe and functional in CHF patients. It is also hypothesized that quantitative measurements of intravascular plasma volume status and GFR will differ from standard clinical assessments and estimating equations, and that clinical decision making would have been improved in a subpopulation of patients had the quantitative measurements delivered by the FAST PV and mGFR Technology™ been available to the physician during the course of care.

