
Rationale
	
Previous clinical studies have shown the FAST technology to be safe and functional in patients with chronic kidney disease (CKD) and in healthy subjects. The technology has not been studied in CHF patients. In previous clinical studies, the technology has been demonstrated to accurately measure PV and mGFR in patients with CKD and healthy patients when compared to other clinical techniques including, estimated glomerular filtration rate (eGFR) calculations, Iohexol clearance and Nadler's formula. Additionally, previous studies have shown that the concentration of the PV marker remains relatively constant during the first two hours after injection, given that this high-molecular weight marker is predicted to exclusively occupy the intravascular compartment and exhibit a long half-life.
 
In this study, the safety and functionality of the FAST Technology will be evaluated in CHF patients. The non-clinical and clinical history of the product provides confidence that the

	
technology will be well tolerated and function correctly in the CHF population.
 
The blood samples are timed to maximize the information gathered during the study. In addition to measurements of PV and GFR, FAST will determine the technology's functionality by comparing the concentration of the PV marker at the 15, 30 and 60 minute time points. It is not believed that the plasma volume will change significantly within that time period and thus the concentration of the PV marker should remain relatively constant.

Study medication (IMP) / Therapeutic strategy	
Visible fluorescent injectate (VFI) (FD004), Powder for Solution for Injection, 47 mg. VFI is diluted with Water for Injection and a total of 3 mL of VFI is administered by bolus injection. There is 47 mg of VFI administered in this 3 mL dose (35 mg of FD001 and 12 mg of FD003). VFI is dosed on Day 1 and Day 3 approximately 48 hours apart.

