l See Table 10 for the Adjudication Committee Evaluation Questions; Adjudication Committee meets after all collected data available.

m See Table 11 for Details of Pregnancy test

\*will be collected retrospectively after study inclusion

Study objectives / endpoints	
Primary endpoint: Global aim is to assess the safety and function of the FAST PV and mGFR Technology in hospitalized patients with heart failure.
 
 
• Safety will be assessed by determination of the absolute and relative frequencies of AEs and SAEs related to VFI.
 
• Function of the FAST PV measurement will be assessed by determining the plasma stability of the FD003 high molecular weight marker over the 15, 30, and 60 minute blood draws and applying the following criteria: 
 
- The FAST PV measurement is considered as stable, if the mean plasma concentration of FD003 at 30 minutes is not more than 10% lower than the mean plasma concentration at 15 minutes AND if the mean plasma concentration at 60 minutes is not more than 10% lower than the mean plasma concentration at 30 minutes
 
- We will determine the percentage of patients which show a decline in the plasma concentration of FD003 of more than 10% from 15min to 30min and separately from 30 min to 60min. This percentage should be ideally close to 0.
 
 
 
 
Secondary Endpoints:
 
 
• To evaluate how estimated PV (ePV) and estimated total blood volume (TBV) assessments on days 1 and 3 (by established measures such as Nadler's formula or Metropolitan Life Tables) predict measured PV (mPV; as assessed by FAST methodology) and measured TBV (mTBV; calculated from mPV and measured hematocrit) at these time points.
 
• To evaluate how a clinical evaluation (including a reasonable subset of the variables age, gender, BMI, hematocrit, edema grade, presence of pulmonary rales, presence of jugular venous congestion, arterial blood pressure, NYHA stage, respiratory rate) on days 1 and 3 predicts mPV and mTBV at these time points.
 
• To evaluate whether eGFR calculation by the CKD-EPI formula on days 1 and 3 provides an accurate estimate of
 

-------------------------------------	---

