### 3.1.2 Investigational Product Background

The IV administered visible fluorescent injectate (VFI)™ agent is comprised of a mixture of 2 different molecular weight carboxymethyl dextran molecules (5 kD and 150 kD) with different fluorescent dye molecules covalently attached. The 5 kD carboxymethyl dextran (FD001) is labeled with 5-aminofluorescein and the 150 kD carboxymethyl dextran (FD003) is labeled with 2-sulfohexamine rhodamine. These fluorescent labels are covalently attached to the dextran through the carboxymethyl moiety. When combined in a 3:1 (mass) ratio of small to large molecules, these dextrans make up the VFI, termed FD004.

The high molecular weight labeled carboxymethyl dextran, FD003, is not rapidly cleared from the vasculature and is not rapidly cleared by passive filtration in the kidneys; therefore, its concentration in the blood stream after injection provides a direct measurement of the total PV. The low molecular weight labeled carboxymethyl dextran, FD001, is also not patient to rapid metabolism but is freely filtered by the kidneys. The decline in the concentration of FD001 combined with the PV measured by FD003 provides a rapid and accurate assessment of GFR.

The VFI is administered IV through a bolus injection.

While the VFI is a substantially modified dextran-based compound, other dextran products have, on rare occasions, been associated with mild to severe, acute anaphylactic reactions including death. As a precaution, patients will be closely monitored for signs of allergy and anaphylaxis, and an emergency resuscitation kit

and team will be available within the clinical research unit (CRU) throughout the treatment period.

Fluorescent dyes such as fluorescein, which is also used in the VFI, are known to cause transient ocular light sensitivity, although this effect was not reported at any dose studied in any of the previous human clinical studies. Should this effect be observed, patients will be provided with disposable protective sunglasses to wear until the effect is reversed.

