#### **3.1.3.4 Phase 2b Study at University of Alabama at Birmingham and ICON**

The Phase 2b study was a prospective, open-label study designed to evaluate the safety, tolerability, PK, and pharmacodynamics (PD) of FAST PV and mGFR Technology in healthy patients and patients with varying degrees of renal impairment. A total of 32 patients were planned to be enrolled in 4 cohorts of up to 8 patients/patients each. Healthy patients in Cohorts 1 and 2 had an  $eGFR \geq 60$  mL/min/1.73 m^2; patients with impaired renal function in Cohort 3 had an  $eGFR \geq 30$  and  $< 60$  mL/min/1.73 m^2; and patients with impaired renal function in Cohort 4 had an  $eGFR \geq 15$  and  $< 30$  mL/min/1.73 m^2. Patients in Cohort 1 received a single dose of VFI followed 130 minutes later by a 350 mL infusion of 5% albumin in normal saline over 30 minutes on day 1. Patients in Cohort 2 received a dose of VFI followed 160 minutes later by a single dose of iohexol on day 1 and a second dose of VFI 24 hours following the initial dose of VFI. Patients in Cohorts 3 and 4 received a single dose of VFI followed 160 minutes later by a single dose of iohexol on day 1.

The pharmacokinetics of FD001 and FD003 showed that the clearance of FD001 was proportional to kidney function with urine clearances of 59.955 mL/min, 25.919 mL/min and 12.635 mL/min for cohorts 2, 3, and 4 respectively, when using 0 to 2 hour data. Following the end of the bolus injection, the plasma concentration of the FD001 decreased following a multi-exponent and first order elimination curve. Average measured GFR for cohorts 2, 3 and 4 were 87 mL/min, 48 mL/min, and 27 mL/min respectively.

The FD003 volume estimates indicated that FD003 appeared to occupy a volume of space equal to the plasma volume (Figure 4). FD003 had determined elimination half-lives of 95.3, 99.1, and 106 hours for Cohorts 2, 3, and 4, respectively. These rates were similar across the renal functions studied which indicates the marker's non-renal clearance is preserved in kidney failure patients.

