### 7.6 Primary analysis

Safety will be assessed by determination of the absolute and relative frequencies of AEs and SAEs related to VFI. Related AEs and SAEs include all events that are sure, probable and possible related.

Function of the FAST PV measurement will be assessed by determining the plasma stability of the FD003 high molecular weight marker over the 15, 30, and 60 minute blood draws at day 1 and 3 and applying the following criteria:

- The FAST PV measurement is considered as stable, if the mean plasma concentration of FD003 at 30 minutes is not more than 10% lower than the mean plasma concentration at 15 minutes AND if the mean plasma concentration at 60 minutes is not more than 10% lower than the mean plasma concentration at 30 minutes. The frequency of patients with stable FD003 plasma concentration will be analyzed descriptively for day 1 and day 3.
- The absolute and relative frequency of patients which show a decline in the plasma concentration of FD003 of more than 10% from 15 minutes to 30 minutes and separately from 30 minutes to 60 minutes will be determined for day 1 and day 3.

Further, the change (absolute and relative) in plasma concentration of FD003 from 15 to 30 minutes, and from 30 to 60 minutes will be displayed descriptively for day 1 and day 3 separately.

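### The primary aim covers function of the PV and mGFR technology, but both function criteria use the PV marker only and no analysis tests mGFR against a limit or an independent standard

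*Protocol*

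**What the plan says.** The wide scope appears in the Synopsis (Hypotheses): "It is hypothesized that utilizing the FAST PV and mGFR Technology™ is safe and functional in CHF patients". The primary aim in the Synopsis, Protocol 4.1 and Section 14, and SAP 4.2 and 7.1 likewise names PV and mGFR together; in the Synopsis it reads: "Global aim is to assess the safety and function of the FAST PV and mGFR Technology in hospitalized patients with heart failure".

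The function endpoint is narrower. SAP 7.6 states: "Function of the FAST PV measurement will be assessed by determining the plasma stability of the FD003 high molecular weight marker". It has two criteria:

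- On means: "The FAST PV measurement is considered as stable, if the mean plasma concentration of FD003 at 30 minutes is not more than 10% lower" than at 15 minutes, with the same rule from 30 to 60 minutes.
- On patients: "The absolute and relative frequency of patients which show a decline in the plasma concentration of FD003 of more than 10" per cent, counted for each interval.

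The Synopsis (Rationale) and Protocol 3.2.2 then let the narrow test speak for the whole technology: "FAST will determine the technology's functionality by comparing the concentration of the PV marker at the 15, 30 and 60 minute time points".

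Protocol 3.1.2 explains why the two halves differ: "The decline in the concentration of FD001 combined with the PV measured by FD003 provides a rapid and accurate assessment of GFR". So mGFR needs both markers, whereas the function criteria look at one.

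**The concern.** A stable FD003 concentration is needed for a valid mGFR but is not enough for one. An error in the FD001 assay, in the modelling of the FD001 decline or in the GFR algorithm leaves FD003 untouched. If the report concludes on function in the terms of the primary aim, it would cover a measurement for which the trial planned no evidence, in a population where the protocol says the technology has not been studied.

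The secondary analyses do not close the gap. SAP 7.7.1 asks whether eGFR is accurate against mGFR, with mGFR as the reference. The hypothesis also predicts that measured GFR will differ from the estimating equations. A disagreement caused by mGFR would therefore count against eGFR and appear to fit the hypothesis.

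Only function is affected. The safety assessment concerns the injectate as a whole.

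**Working it through.** The plan has no sample-size figure to reproduce: 50 patients were set by feasibility, without alpha, power or effect size. The check is a trace of both markers through the analyses, with a small illustration.

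**1. Primary function criteria.** FD003 enters both; FD001 enters 0 of 2.

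**2. What FD003 is expected to do.** The protocol's earlier studies give FD003 half-lives between 47 h (3.1.3.2) and 125 h (3.1.3.3). Expected decline = 1 − 0.5^(interval / half-life).

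| Half-life | 15 to 30 min (0.25 h) | 30 to 60 min (0.5 h) |
|---|---|---|
| 47 h | 1 − 0.5^(0.25/47) = 0.37% | 1 − 0.5^(0.5/47) = 0.73% |
| 125 h | 1 − 0.5^(0.25/125) = 0.14% | 1 − 0.5^(0.5/125) = 0.28% |

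If elimination in CHF is similar, FD003 sits far inside the 10% margin whatever FD001 does.

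**3. Every planned use of mGFR.**

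| Use (SAP 7.7.1) | Role of mGFR | Limit or independent standard for mGFR? |
|---|---|---|
| eGFR accuracy: regression, Bland-Altman with ±6 ml/min, diagnostic accuracy | Reference | No; the limits judge eGFR |
| AKI | Predictor, as mGFR/eGFR ratio | No |
| Change in eGFR | Predictor, as change in mGFR | No |
| Change in mGFR by volume group | Outcome | No |
| Improving versus worsening mGFR | Grouping variable | No |
| Adjudication committee | Information supplied | No |

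**4. Illustration.** One simulated data set, n = 50. Assumptions, not figures from the documents: true GFR uniform from 15 to 90 ml/min, eGFR error 20%, day-to-day GFR variation 15%, FD003 assay error 3%. The FD003 half-life is 95.3 h (Phase 2b, Cohort 2). Only mGFR is altered, so the FD003 columns are equal by construction. That is the point at issue.

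| mGFR | Mean FD003 decline, two intervals | Patients above 10% | Mean eGFR − mGFR, Day 1 (ml/min) | Ratio below 1 | Rank accuracy |
|---|---|---|---|---|---|
| Correct | 0.5%, 0.8% | 0, 0 | −0.5 | 23 of 50 | 0.851 |
| × 1.5 | 0.5%, 0.8% | 0, 0 | −27.5 | 1 of 50 | 0.851 |
| × 0.5 | 0.5%, 0.8% | 0, 0 | +26.5 | 50 of 50 | 0.851 |
| Shuffled between patients | 0.5%, 0.8% | 0, 0 | −0.5 | 21 of 50 | 0.513 |

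A constant proportional error cancels from rank accuracy, from the lowest-quartile ratio group and from the percentage change between Day 1 and Day 3. It shows in the Bland-Altman bias and in the ratio-below-1 count. Shuffling lowers rank accuracy. With mGFR as the reference, the shifted bias and the lower rank accuracy would be read as eGFR performing badly.

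**5. Room for a descriptive mGFR count.** With 50 patients per dosing day, exact 95% intervals for a share are 0 to 7.1% for 0/50, 3.3 to 21.8% for 5/50 and 66.3 to 90.0% for 40/50. Such a count is informative at the planned size.

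**The case against.** The strongest reply is that the plan already labels its endpoint as function of the PV measurement, and that its only written verdict is that this measurement is stable. Protocol Section 14 and SAP 7.1 add that function cannot rest on one endpoint and that everything is descriptive. That is fair, and it rules out one tempting inference: that a faulty mGFR would be declared functional. No rule turns the PV result into an mGFR verdict. But no rule prevents it either, and the rationale text equates the two.

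A reader might also infer that mGFR only ever serves as the reference. The trace above shows otherwise. Its links with AKI and with later eGFR change could give indirect support, though without any limit for success.

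Earlier studies compared FAST with iohexol, and Protocol 3.1.3.3 gives a reason to omit iohexol when GFR is changing. That reason was given for an earlier AKI cohort, though it may apply here. It explains the missing external standard but not the absence of any FD001-based criterion. The cystatin C formulas in the SAP bring in a second filtration marker, but they are estimates and are not used to judge mGFR.

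A reader might see proof of bias in Phase 2b, where FD001 urine clearances of 59.955, 25.919 and 12.635 mL/min stand beside this: "Average measured GFR for cohorts 2, 3 and 4 were 87 mL/min, 48 mL/min, and 27 mL/min respectively". The documents do not support that. Protocol 3.1.3.4 does not state how measured GFR was obtained, and those cohorts also received iohexol. Phase 2a puts early FD001 distribution as complete only at 8 to 12 hours, so a 0 to 2 hour clearance need not equal GFR. These figures do not size the problem.

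Nor would comparing mGFR from draws up to 60 minutes with mGFR including the 180-minute draw settle it. A shared proportional error cancels, incomplete distribution confounds the comparison, and the documents do not show that a 60-minute mGFR can be computed.

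**Conclusion.** The concern holds as a mismatch between claim and evidence. The hypothesis and primary aim cover PV and mGFR, none of the two function criteria involves FD001, and no analysis sets mGFR against an acceptance limit or an independent standard. A fault confined to mGFR cannot alter the primary function result, and in the eGFR accuracy analysis it would be attributed to eGFR.

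The documents do not show that mGFR is biased, and this point does not say so. It says only that the trial cannot establish mGFR function. The count of criteria and the trace of uses rest on the text alone. The simulated values depend on the stated assumptions, but the independence of the FD003 criteria from FD001 does not. An mGFR fault that came from FD003 instability could still show in the primary result.

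**What to change.** 1. In the Synopsis (Hypotheses, Rationale, Study objectives), Protocol 3.2.2, 4.1 and Section 14, and SAP 4.2 and 7.6, state that the primary function conclusion applies to the PV measurement only and that this trial does not establish mGFR function. SAP 7.1 repeats the aim and should follow.
2. In SAP 7.7.1, report eGFR against mGFR as agreement or disagreement between two methods, not as accuracy of eGFR. The planned statistics can stay.
3. In SAP 7.5, beside the PV count already planned, add the number and share of dosing days with an evaluable mGFR. Show Day 1 and Day 3 separately, since the two days come from the same patients, and define evaluable before the data review meeting.

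The cost is wording and one descriptive count, with no further samples, visits or patients. The downside is a narrower primary claim. The count shows whether mGFR can be obtained, not whether it is right.

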## 2 Flow-Chart

## 3 Introduction

### 3.1 Introduction and background

A rapid and accurate measurement of plasma volume (PV) and glomerular filtration rate (GFR) is important in acute kidney injury (AKI) and chronic kidney disease (CKD) for assessment of impairment, diagnosis, and prompt treatment.

Reductions in PV and/or GFR secondary to kidney injury, either acute or chronic, are accompanied by increases in blood urea nitrogen (BUN) and serum creatinine ( $S_{cr}$ ) levels. Currently, either  $S_{cr}$ , or an equation based on  $S_{cr}$ , is used to determine a patient's estimated GFR (eGFR). Unfortunately, these 2 approaches are not reliable over the full range of GFR, and neither can be used for early detection or functional assessment in patients with a rapidly changing GFR, such as patients with AKI.

Recent data indicate that even very small changes in  $S_{cr}$ , which were previously thought to be clinically insignificant, are now known to predict an increased mortality rate. A technique to measure PV and GFR rapidly would be valuable to detect the loss of kidney function that leads to these acute changes in  $S_{cr}$  so that treatment can begin as soon as possible.

Glomerular filtration rate is the most clinically relevant metric for understanding renal function, as it is the rate by which the kidney is able to filter waste products in the bloodstream. Accurate measurement of GFR in acutely ill patients could also facilitate accurate dosing of drugs to maximize therapeutic efficacy while minimizing toxicity. Therefore, technical advances in this field are of major clinical importance, especially in high-risk patients where intense surveillance is necessary.

### 3.1.1 Investigational Device Background

The FAST PV and mGFR Technology™ is a direct measurement of PV and GFR that relies on reading the concentration of fluorescent markers attached to different size dextran molecules introduced into the bloodstream. The test is intended as an adjunct to current methods utilized to assess kidney function.

The FAST PV and mGFR Technology includes intravenously (IV) administered fluorescent markers, timed blood draws, a validated fluorometric assay, and a computed algorithm to integrate the results and calculate the GFR.

The FAST PV and mGFR Technology will aid in identifying and determining the extent of renal dysfunction, therefore promoting early treatment, including dialysis initiation, as well as enrollment and stratification for clinical studies. It could also be used to determine the effect of a clinical maneuver on GFR such as volume resuscitation.

In addition to measuring the GFR, the FAST PV and mGFR technology is capable of measuring the intervacular plasma volume of a patient. With a single dose, the PV can be monitored for change or therapeutic affects for up to 8 hours. It will rapidly determine intravascular volume allowing early pharmacologic and or IV volume expanding treatment, as well as enrollment and stratification for clinical studies, and prognostic information. Measurement of PV will allow for accurate therapeutic use of volume expansion or vasopressors in the ICU, especially in patients with endothelial injury as and increased vascular permeability as in sepsis.

### 3.1.2 Investigational Product Background

The IV administered visible fluorescent injectate (VFI)™ agent is comprised of a mixture of 2 different molecular weight carboxymethyl dextran molecules (5 kD and 150 kD) with different fluorescent dye molecules covalently attached. The 5 kD carboxymethyl dextran (FD001) is labeled with 5-aminofluorescein and the 150 kD carboxymethyl dextran (FD003) is labeled with 2-sulfohexamine rhodamine. These fluorescent labels are covalently attached to the dextran through the carboxymethyl moiety. When combined in a 3:1 (mass) ratio of small to large molecules, these dextrans make up the VFI, termed FD004.

The high molecular weight labeled carboxymethyl dextran, FD003, is not rapidly cleared from the vasculature and is not rapidly cleared by passive filtration in the kidneys; therefore, its concentration in the blood stream after injection provides a direct measurement of the total PV. The low molecular weight labeled carboxymethyl dextran, FD001, is also not patient to rapid metabolism but is freely filtered by the kidneys. The decline in the concentration of FD001 combined with the PV measured by FD003 provides a rapid and accurate assessment of GFR.

The VFI is administered IV through a bolus injection.

While the VFI is a substantially modified dextran-based compound, other dextran products have, on rare occasions, been associated with mild to severe, acute anaphylactic reactions including death. As a precaution, patients will be closely monitored for signs of allergy and anaphylaxis, and an emergency resuscitation kit

and team will be available within the clinical research unit (CRU) throughout the treatment period.

Fluorescent dyes such as fluorescein, which is also used in the VFI, are known to cause transient ocular light sensitivity, although this effect was not reported at any dose studied in any of the previous human clinical studies. Should this effect be observed, patients will be provided with disposable protective sunglasses to wear until the effect is reversed.

